6 SAFETY CONSIDERATIONS

6.1 Complaints and Adverse Events

Complaints

A complaint is any written, electronic, or oral communication that alleges deficiencies related to the physical characteristics, identity, quality, purity, potency, durability, reliability, safety, effectiveness, or performance of a product/device. Complaints associated with any component of this investigational product must be reported to AbbVie.

Product Complaint

A product complaint is any complaint related to the biologic or drug component of the product or to the medical device component(s).

For a product this may include, but is not limited to, damaged/broken product or packaging, product appearance whose color/markings do not match the labeling, labeling discrepancies/inadequacies in the labeling/instructions (e.g., printing illegible), missing components/product, device damage or not working properly, or packaging issues.

Product complaints concerning the investigational product and/or device must be reported to AbbVie within 24 hours of the study site's knowledge of the event.

Reporting will be done via electronic data capture (EDC). The date the product complaint details are entered into EDC and the form is saved represents the date reported to AbbVie. A back-up paper form will be provided for reporting complaints related to unassigned product or in the event of an EDC system issue. If a back-up paper form is used, the date the form is emailed to [contact] represents the date reported to AbbVie.

All follow-up information is to be reported to the sponsor (or an authorized representative) and documented in source as required by the sponsor. Product complaints associated with AEs will be reported in the study summary. All other complaints will be monitored on an ongoing basis. Product complaints occurring during the study will be followed up to a satisfactory conclusion.

Medical Complaints/Adverse Events and Serious Adverse Events: Linaclotide

An AE is defined as any untoward medical occurrence in a subject or clinical investigation subject administered a pharmaceutical product and which does not necessarily have a causal relationship with this treatment. An AE can therefore be any unfavorable and unintended sign (including an abnormal laboratory finding), symptom, or disease temporally associated with the use of a medicinal (investigational) product, whether or not the event is considered causally related to the use of the product.

Such an event can result from use of the drug as stipulated in the protocol or labeling, as well as from "special situations" such as accidental or intentional overdose, medication error, occupational or accidental exposure, off-label use, drug abuse, drug misuse, or drug withdrawal, all which must be reported whether associated with an AE or not. Any worsening of a pre-existing condition or illness is

considered an AE. Worsening in severity of a reported AE should be reported as a new AE. Laboratory abnormalities and changes in vital signs are considered to be AEs only if they result in discontinuation from the study, necessitate therapeutic medical intervention, meets protocol-specific criteria (see Section 6.2 regarding toxicity management), and/or if the investigator considers them to be AEs.

The investigators will monitor each subject for clinical and laboratory evidence of AEs on a routine basis throughout the study. All AEs will be followed to a satisfactory conclusion.

An elective surgery/procedure scheduled to occur during a study will not be considered an AE if the surgery/procedure is being performed for a pre-existing condition and/or the surgery/procedure has been pre-planned prior to study entry. However, if the pre-existing condition deteriorates unexpectedly during the study (e.g., surgery performed earlier than planned), then the deterioration of the condition for which the elective surgery/procedure is being done will be considered an AE.

If an AE, whether associated with study drug or not, meets any of the following criteria, it is to be reported to AbbVie clinical pharmacovigilance as a SAE within 24 hours of the site being made aware of the SAE (refer to Section 4.2 of the Operations Manual for reporting details and contact information):

Death of Subject	An event that results in the death of a subject.
Life-Threatening	An event that, in the opinion of the investigator, would have resulted in immediate fatality if medical intervention had not been taken. This does not include an event that would have been fatal if it had occurred in a more severe form.
Hospitalization or Prolongation of Hospitalization	An event that results in an admission to the hospital for any length of time or prolongs the subject's hospital stay. This does not include an emergency room visit or admission to an outpatient facility.
Congenital Anomaly	An anomaly detected at or after birth, or any anomaly that results in fetal loss.
Persistent or Significant Disability/Incapacity	An event that results in a condition that substantially interferes with the activities of daily living of a study subject. Disability is not intended to include experiences of relatively minor medical significance such as headache, nausea, vomiting, diarrhea, influenza, and accidental trauma (e.g., sprained ankle).

**Important Medical Event
Requiring Medical or Surgical
Intervention to Prevent
Serious Outcome**

An important medical event that may not be immediately life-threatening or result in death or hospitalization, but based on medical judgment may jeopardize the subject and may require medical or surgical intervention to prevent any of the outcomes listed above (i.e., death of subject, life threatening, hospitalization, prolongation of hospitalization, congenital anomaly, or persistent or significant disability/incapacity). Additionally, any elective or spontaneous abortion or stillbirth is considered an important medical event along with any suspected transmission of an infectious agent via a medicinal product if no other serious criterion is applicable. Examples of such events include allergic bronchospasm requiring intensive treatment in an emergency room or at home, blood dyscrasias or convulsions that do not result in inpatient hospitalization, or the development of drug dependency or drug abuse.

All adverse events reported from the time of study drug administration up to 30 days, after discontinuation of study drug administration will be collected, whether solicited or spontaneously reported by the subject. After 30 days, following the last dose of study drug or completion of study treatment only spontaneously reported SAEs will be collected (nonserious AEs will not be collected). In addition, study procedure-related serious and nonserious adverse events will be collected from the time the subject signs the study-specific informed consent.

The following definitions will be used for Serious Adverse Reactions (SAR) and Suspected Unexpected Serious Adverse Reaction (SUSAR):

SAR	Defined as all noxious and unintended responses to an IMP related to any dose administered that result in an SAE as defined above.
SUSAR	Refers to individual SAE case reports from clinical trials where a causal relationship between the SAE and the IMP was suspected by either the sponsor or the investigator, is unexpected (not listed in the applicable Reference Safety Information), and meets one of the above serious criteria.

AbbVie will be responsible for SUSAR reporting for the Investigational Medicinal Product (IMP) in accordance with global and local requirements.

Adverse events will be monitored throughout the study to identify any of special interest that may indicate a trend or risk to subjects.

Adverse Events of Special Interest

The following AESI will be monitored during the study:

- Clinically significant (per investigator's discretion) dehydration due to diarrhea causing hospitalization, which is considered by the investigator or sponsor to be related to the study drug.

- Clinically significant (per investigator's discretion) electrolyte abnormalities due to diarrhea, which is considered by the investigator or sponsor to be related to the study drug.
- Clinically significant (per investigator's discretion) ECG abnormalities due to diarrhea, which is considered by the investigator or sponsor to be related to the study drug.

The investigator should contact the sponsor if there is any question whether the criteria for an AESI have been met.

To ensure the safety of the subjects, children will be carefully monitored for safety and tolerability. Legally authorized representative/parents/guardians will be instructed to stop the drug and contact the investigator in case of the onset of any AESI. Additionally, the occurrence of intolerable diarrhea (as assessed by the investigator), will be reported to the sponsor. Intolerable diarrhea and all AE data will be monitored by the DSMB, who, based on the frequency and severity of the events, could recommend halting the administration of investigational product (refer to Section [5.10](#) for additional details).

Adverse Event Severity and Relationship to Study Drug

The investigator will rate the severity of each AE according to the NCI CTCAE (Version 4.03)

The investigator will use the following definitions to assess the relationship of the AE to the use of study drug:

Reasonable Possibility	After consideration of factors including timing of the event, biologic plausibility, clinical judgment, and potential alternative causes, there is sufficient evidence (information) to suggest a causal relationship.
No Reasonable Possibility	After consideration of factors including timing of the event, biologic plausibility, clinical judgment, and potential alternative causes, there is insufficient evidence (information) to suggest a causal relationship.

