- f. Protocol-permitted rescue medication (outlined in Section 5.3 of the protocol) will be site-supplied or site-dispensed from preintervention to Week 4 (Visits 2-5). The LAR/parent/guardian may choose a different protocol-permitted rescue medication at any subsequent visit, where available. Additional protocol permitted rescue medications may be site-supplied or site-dispensed as needed at any subsequent visits, where available. Subject must not have used rescue medication until randomized; this includes the calendar day before the enrollment/randomization visit and on the day of the enrollment/randomization visit prior to enrollment/randomization.
- g. Rescue medication will be recorded, refer to Section 3.3 for details.
- h. IWRS will be contacted to obtain the study drug (bottle number) to be dispensed. Study drug will be prepared by parent/caregiver at the site after instructions how to prepare IP solution have been explained and video reviewed. LAR/parent/guardian will administer first study drug at the study site. Site will document training and first dose preparation by parent/caregiver, as also administration. Subjects may eat 15 - 30 minutes after dosing.

WEEK 2 (Study Intervention Period – Visit 4 Day 15

[± 2 Days]):

INTERVIEW	
 Assess Rome IV status^a Adverse event assessment Prior/concomitant therapy
Observer Reported Outcome	
 eDiary Compliance^b
EXAMS	
 Vital signs (including weight) and Postural Vital Signs^c Physical examination
CENTRAL LAB	
 Blood samples for PK assay (optional)^d
TREATMENT^e	
 Rescue Medication^{f,g} IP Compliance and Accountability

NOTE: All procedures must be performed onsite. All assessments must be recorded in the source records in addition to the eCRF.

- a. Prior to dosing, the investigator or appropriate site staff member will assess if Rome IV criteria for FC was met and record the outcome in the eCRF. Eligibility for the study is not based on this assessment.

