- b. Study site staff will verify compliance with the eDiary and remind LAR/parent/guardian/caregivers to complete their assessments daily. Assessment of global change in symptoms and global severity of symptoms will be completed in the weekly Diary. The global severity items will be completed beginning at the Preintervention Period through the 1-week postintervention visit (Visit 6), and the global change items will be completed from one week after enrollment/randomization through the 1-week postintervention visit (Visit 6).
- c. Vital signs include weight, temperature, and respiratory rate. Postural vital signs (supine and standing whenever possible according to subject's age) include pulse rate and systolic and diastolic blood pressure. Blood pressure and pulse measurements should be preceded by at least 5 minutes of rest for the subject in a quiet setting. At all visits, postural vital signs must be obtained after subjects have been in a supine position for at least 2 to 3 minutes, followed by a standing position for at least 1 minute. If possible, temperature should be obtained using the same method at each visit.
- d. The optional PK sample can be collected either before or after subjects receive study drug. Optional PK samples should be collected at the same time as clinical labs. This visit should be scheduled at approximately the same time as when subjects take their daily dose. Refer to Section 3.8 for additional details.
- e. The subject must complete at least 4 weeks (28 days) of intervention period before returning for the Week 4/Day 29 EOT or premature discontinuation visit (Visit 5). The study drug will be administered at approximately the same time as on other days of study drug administration.
- f. Protocol-permitted rescue medication (outlined in Section 5.3 of the protocol) will be site-supplied or site-dispensed from preintervention to Week 4 (Visits 2-5). The LAR/parent/guardian may choose a different protocol-permitted rescue medication at any subsequent visit, where available. Additional protocol permitted rescue medications may be site-supplied or site-dispensed as needed at any subsequent visits, where available.
- g. Rescue medication will be recorded, refer to Section 3.3 for details.

WEEK 4 (Visit 5 Day 29 EOT or premature
discontinuation [+ 2 Days]):

INTERVIEW	
 • Rome IV Assessment • Assess Rome IV status^a • Adverse event assessment • Prior/concomitant therapy

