Observer Reported Outcome	
 • eDiary Compliance^b
EXAMS	
 • Vital signs (including weight) and Postural Vital Signs^c • Physical examination^d • ECG (single)
CENTRAL LAB	
 • Blood samples for PK assay (optional)^f • Clinical chemistry, Hematology (CBC)^e
TREATMENT	
 • Rescue Medication^{h,i} • IP Compliance and Accountability

NOTE: All procedures must be performed onsite. All assessments must be recorded in the source records in addition to the eCRF.

- a. Prior to dosing, the investigator or appropriate site staff member will assess if Rome IV criteria for FC was met and record the outcome in the eCRF. Eligibility for the study is not based on this assessment. Refer to Section 3.5 for details.
- b. Study site staff will verify compliance with the eDiary and remind LAR/parent/guardian/caregivers to complete their assessments daily. Assessment of global change in symptoms and global severity of symptoms will be completed in the weekly Diary. The global severity items will be completed beginning at the Preintervention Period through the 1-week postintervention visit (Visit 6), and the global change items will be completed from one week after enrollment/randomization through the 1-week postintervention visit (Visit 6).
- c. Vital signs include weight, temperature, and respiratory rate. Postural vital signs (supine and standing whenever possible according to subject's age) include pulse rate and systolic and diastolic blood pressure. Blood pressure and pulse measurements should be preceded by at least 5 minutes of rest for the subject in a quiet setting. At all visits, postural vital signs must be obtained after subjects have been in a supine position for at least 2 to 3 minutes, followed by a standing position for at least 1 minute. If possible, temperature should be obtained using the same method at each visit.
- d. Physical examinations will be performed by medically qualified site personnel at Screening (Visit 1), enrollment/randomization (Visit 3), Week 2 (Visit 4), and Week 4 (Visit 5), physical exams may be repeated at the investigator's discretion. If fecal impaction (defined as a hard mass in the lower abdomen identified on physical examination or a dilated rectum filled with a large amount of stool on rectal examination) is documented during an optional repeat physical examination, the study physician must be notified.

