- e. Clinical laboratory tests consist of clinical chemistry and hematology. All laboratory tests requiring blood draws should be collected at the same time.
- f. The optional PK sample can be collected either before or after subjects receive their last dose of study drug. Optional PK samples should be collected at the same time as clinical labs. This visit should be scheduled at approximately the same time as when subjects take their daily dose.

- g. Protocol-permitted rescue medication (outlined in Section 5.3 of the protocol) will be site-supplied or site-dispensed from preintervention to Week 4 (Visits 2-5). The LAR/parent/guardian may choose a different protocol-permitted rescue medication at any subsequent visit, where available. Additional protocol permitted rescue medications may be site-supplied or site-dispensed as needed at any subsequent visits, where available. Subject must not have used rescue medication until randomized; this includes the calendar day before the enrollment/randomization visit and on the day of the enrollment/randomization visit prior to enrollment/randomization.
- h. All enrolled/randomized subjects who prematurely discontinue from the study, regardless of cause, should be seen for the assessments completed at EOT (Visit 5, Week 4).
- i. Rescue medication will be recorded, refer to Section 3.3 for details.

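### The caregiver's instruction to stop drug is tied to AESI onset, which a caregiver cannot recognise before the child is hospitalized; separately, two Visit 4 laboratory references need correcting

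*Protocol*

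**What the plan says.** Protocol 6.1 states that caregivers "will be instructed to stop the drug and contact the investigator in case of the onset of any AESI". It defines three AESIs, each subject to clinical significance at the investigator's discretion:

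- "dehydration due to diarrhea causing hospitalization, which is considered by the investigator or sponsor to be related to the study drug";
- "electrolyte abnormalities due to diarrhea, which is considered by the investigator or sponsor to be related to the study drug";
- ECG abnormalities due to diarrhea, with the same causality condition.

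Protocol 5.5 makes an AESI a mandatory reason for discontinuation and, like 6.2, repeats the hospitalization condition.

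On the laboratory schedule, the Week 2 (Visit 4) list in Operations Manual 2.1 has one laboratory item: "Blood samples for PK assay (optional". Footnote d to that visit then says "Optional PK samples should be collected at the same time as clinical labs". Operations Manual Appendix B, under Clinical Laboratory Tests, names Visit 4 with a window of plus 2 days as the example for rescheduled draws.

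**The concern.** A stop-and-call instruction is useful if the person holding the bottle can tell when it applies. Here that person is a parent who prepares and gives the dose at home to a child under 2 years. Protocol 2.2 names diarrhea as the most common adverse reaction in earlier studies. If the trigger is something the parent cannot see, or sees only once the child is in hospital, the instruction cannot act as a precaution. The harm to be prevented is continued dosing of an infant who is becoming dehydrated.

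The laboratory text is a smaller matter. A site that reads the Visit 4 footnote literally could draw clinical blood at Week 2, while a site that follows the visit list would not.

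**Working it through.** No formula or plan figure is at issue, so the check sets the texts side by side.

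**Can a caregiver recognise an AESI at onset?** (Protocol 6.1)

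- Dehydration: a hospitalization is part of the definition. A caregiver sees that, but only when it has happened.
- Electrolytes: needs a blood chemistry result.
- ECG: needs a recording and a reading.
- All three: need the investigator's view of significance and the investigator's or sponsor's view of causality.

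Count: two of three need a test result, one of three needs a hospitalization, and none of three can be recognised by a caregiver beforehand. SAP 10.2.5 words the first as volume depletion without hospitalization, but it too rests on investigator or sponsor judgement, and Protocol 6.1 governs conduct.

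**Is the stop earlier than the event it should prevent?** Protocol 5.5 requires discontinuation for an AESI. The caregiver's stop therefore comes no earlier than the event that ends the child's participation.

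**Does anything else act sooner?** Yes, through the investigator:

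- interruption for poor tolerability, as the investigator determines (5.4);
- interruption of up to 3 consecutive days for tolerability or AEs (6.2);
- intolerable diarrhea, as the investigator assesses it (6.1, 6.2);
- optional discontinuation for an intolerable AE (5.5).

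Each needs the investigator to know first. The visit after Day 1 is Visit 4 at Day 15 ± 2, that is Day 13 to Day 17, or 12 to 16 days after the first dose. In between, the investigator depends on the caregiver to call.

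**Visit 4 laboratory text** (Operations Manual 2.1 and Appendix B)

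- Chemistry and hematology are listed at Screening and at Visit 5 ("Clinical chemistry, Hematology (CBC"), not at Visit 4.
- The sentence pairing PK samples with clinical laboratory tests also appears at Visit 5, after "The optional PK sample can be collected either before or after subjects receive their last dose of study drug". There it fits, because chemistry is listed.
- Visit 4 has a window of ± 2 days. The plus-2-day window belongs to Visit 5, whose heading reads "discontinuation [+ 2 Days".

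Both mismatches look like text carried between visits. The activity table in Protocol Appendix D is damaged in extraction and was not relied on.

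**What extra interruptions could cost**

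- One full interruption: 3 of 28 dosing days = 10.7% for that child.
- Part 2 linaclotide arm: 12 children at 1:1 gives 6, so 6 × 28 = 168 planned dosing days; one such interruption is 3/168 = 1.8%.
- Part 1: escalation needs at least 5 completers in a cohort of 6 (4.1), so one non-completer is tolerable; two leave 6 − 2 = 4, which is too few.

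**The case against.** The strongest reply is that Protocol 6.1 reports that an instruction will be given; it is not the instruction itself. Consent pages are removed, dosing instructions are supplied separately, and Protocol 6.2 refers AE management to the Operations Manual, part of which is not shown. Symptom-based advice may well exist there. This stands, and it limits the point to the protocol sentence.

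It can also be said that the investigator-run routes act before hospitalization, and that a site could pass on an abnormal result and have the caregiver stop. Both are true. A reader might infer that a child is unprotected until admitted; the documents do not support that. What remains is that these routes start with the investigator, and the one rule addressed to the caregiver gives no sign to act on.

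A reader might also infer that AESIs would go undetected between Screening and Day 29, because chemistry and ECG are scheduled only at Screening and at Visit 5 or premature discontinuation, and that the cohort-stopping rule is therefore unreliable. The documents do not establish this. They allow unscheduled safety samples (Operations Manual 3.15) and symptom-directed examination (3.12), and ask for end-of-treatment assessments in children who discontinue (Protocol 5.5). How often off-schedule tests would be done cannot be judged from the text supplied.

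Finally, a looser trigger has a price: more interruptions, some of which could become discontinuations, and discontinued children are not replaced. This also stands and is counted as a cost under the fix.

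**Conclusion.** The point holds for the wording of Protocol 6.1. Followed literally, the caregiver's stop rule offers no usable trigger before hospitalization: none of three AESI definitions. It is a stated safety measure for infants dosed at home that cannot work as written, and repairing it is inexpensive. It should be fixed, but it does not threaten the trial's analyses.

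The conclusion rests on the supplied text alone. If the caregiver materials already list stop-and-call signs, what remains is to bring 6.1 into line with them.

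The Visit 4 laboratory mismatch is real but editorial. It should not be read as showing that a Week 2 safety draw was intended and then omitted; the visit lists and the windows point to carried-over text.

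**What to change.** Reword the sentence in Protocol 6.1 along these lines:

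> Caregivers will be told to hold study drug and telephone the investigator the same day if the child has repeated watery stools (BSFS type 7; number set by the sponsor), shows signs of dehydration (list set by the sponsor), or is admitted to hospital for any reason. The investigator decides whether dosing resumes under Section 5.4, except that a confirmed AESI or any other mandatory criterion requires discontinuation under Section 5.5.

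The stool count and list of signs are clinical choices that the documents do not settle; they should match the caregiver materials. BSFS type 7 is offered as an example because caregivers already rate stools on that scale in the eDiary.

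Cost: a few more calls and short interruptions. No analysis rule changes, because eDiary data during interruptions are already included as observed (Protocol 7.3, SAP 8.0). Exposure could fall slightly, and a child whose tolerability does not improve must discontinue under 5.4, which matters where 5 of 6 must complete. Setting the stool count with that in mind keeps the effect small.

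For the laboratory text, delete from Visit 4 footnote d the clause tying the PK sample to clinical laboratory tests, and change the Appendix B example from Visit 4 to Visit 5, keeping plus 2 days. This is wording only. Scheduling chemistry at Visit 4 instead would add a venepuncture per child under the 13.5 mL clinical-laboratory limit, and is not needed to resolve the mismatch.
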